2.4.2 Supportive secondary endpoints

2.4.2.1 Efficacy endpoints

All endpoints except insulin dose in this section will be assessed using the FAS and the in-trial observation period and repeated using the on-treatment observation period. Insulin dose will be presented using the safety analysis set and will therefore only use the on-treatment observation period.

Change from baseline in FPG 16 weeks after randomisation

Change from baseline in FPG 16 weeks after randomisation will be analysed based on all planned post baseline measurements until or at 16 weeks after randomisation using a model similar to 1) except with baseline FPG as covariate.

If a subject achieves HbA_{1c} target 16 weeks after randomisation

$HbA_{1c} < 7.0\%$

A dichotomous (responder/non-responder) endpoint will be defined based on whether a subject has met the HbA_{1c} target ($HbA_{1c} < 7.0\%$) 16 weeks after randomisation.

This responder endpoint will be analysed based on a logistic regression model using treatment, region and metformin use at baseline (Yes/No) as factors, and baseline HbA_{1c} as covariate. In analysis of the in-trial observation period subjects without an HbA_{1c} measurement at week 16 will be treated as non-responders. In the analysis using the on-treatment observation period subjects who discontinue randomised treatment, initiate ancillary treatment, withdraw from trial, and/or have no HbA_{1c} measurement at week 16 are included as non-responders.

Statistical Analysis Plan Trial ID: NN1218-4113 UTN: U1111-1180-0636 EudraCT No.: 2016-000878-38

CONFIDENTIAL

Date: Version: Status: Page:

12 February 2019 | Novo Nordisk Final 18 of 29

$HbA_{1c} < 7.0$ % without severe hypoglycaemia

A dichotomous (responder/non-responder) endpoint will be defined based on whether a subject has met the HbA_{1c} target (HbA_{1c} <7.0%) 16 weeks after randomisation without treatment emergent severe hypoglycaemic episodes.

This responder endpoint will be analysed based on a logistic regression model using treatment, region and metformin use at baseline (Yes/No) as factors and baseline HbA_{1c} as covariate. In the analysis of the in-trial observation period subjects without an HbA_{1c} measurement at week 16 will be treated as non-responders. In the analysis using the on-treatment observation period subjects who discontinue randomised treatment, initiate ancillary treatment, withdraw form trial, and/or have no HbA_{1c} measurement at week 16 will be included as non-responders.

Change from baseline in 30- minutes, 1- hour, 2- hour, 3- hour and 4- hour PPG and 30minutes, 2- hour, 3- hour and 4- hour PPG increment 16 weeks after randomisation (meal test)

Laboratory measured PG from the meal test will be analysed for 30 minutes, 1-hour, 2-hours, 3hours and 4-hours PPG separately. The corresponding PPG increments will be derived separately using each PPG measurement minus the pre-prandial PG measurement.

Change from baseline in PPG and PPG increment 16 weeks after randomisation will be analysed separately using a model similar to the model used in hierarchical testing procedure step 2 for 1hour PPG increment 16 weeks after randomisation (meal test) except with the corresponding baseline value as covariate.

Change from baseline in endpoints derived from the 7-9-7-point SMPG profile 16 weeks after randomisation

In general, analyses will be based on the entire 7-9-7-point SMPG profile except for the analyses of nocturnal endpoints where information in the 9-point SMPG profile will be utilised.

PPG and PPG increments based on the 7-9-7-point SMPG profiles will be derived separately for PG measurements made 1 hour after the meal. In the following section this distinction will be considered implicit and without further explanation.

Pre-prandial PG and PPG will be recorded by the subjects as part of the 7-9-7-point SMPG profile prior to three defined visits. Individual mean mealtime PPG (post-breakfast, post-lunch, post-main evening meal) will be derived from the three profiles. Overall mean PPG will be derived from the individual derived mealtime PPG values.

PPG increment for each meal (breakfast, lunch, main evening meal) will be derived from the 7-9-7point SMPG profile as the difference between PPG values and pre-prandial PG values in each

separate profile. The mean of the derived increments will then be calculated separately for each meal. Mean 1 hour PPG increments over all meals will be derived as the mean of all corresponding mean meal increments.

• Change from baseline in mean of the 7-9-7-point SMPG profile

The mean of the 7-9-7-point SMPG profile is defined as the area under the curve profile divided by the measurement time, and is calculated using the linear trapezoidal technique.

Change from baseline in the mean of the 7-9-7-point SMPG profile 16 weeks after randomisation will be analysed based on all planned post baseline measurements until or at 16 weeks after randomisation using a model similar to 1) except with the corresponding baseline value as covariate.

• Change from baseline in PPG and PPG increment (mean, breakfast, lunch and main evening meal)

Change from baseline in PPG and PPG increment endpoints 16 weeks after randomisation for mean over all three meals and the individual meals will be analysed separately based on all planned post baseline measurements until or at 16 weeks after randomisation using a model similar to 1) except with the corresponding baseline value as covariate.

• Fluctuation in 7-9-7-point SMPG profile

The fluctuation in the 7-9-7-point SMPG profile is defined as:

$$\frac{1}{T} \int_{0}^{T} |PG(t) - \overline{PG}| dt$$

where T, PG(t) and \overline{PG} denotes the length of the profile, the PG value at time t and the mean of the profile, respectively. It will be calculated using the linear trapezoidal technique.

Fluctuation in the 7-9-7-point SMPG profile will be logarithmically transformed and analysed based on all planned post baseline measurements until or at 16 weeks after randomisation using a model similar to 1) except with the corresponding log-transformed baseline value as covariate. Estimated treatment means and the estimated treatment differences with corresponding 95% CI will be back-transformed to the original scale, resulting in estimated geometric means, a treatment ratio and a 95% CI for the treatment ratio.

• Change from baseline in nocturnal SMPG measurements

Statistical Analysis Plan		Date:	12 February 2019	Novo Nordisk
Trial ID: NN1218-4113	CONFIDENTIAL	Version:	2.0	
UTN: U1111-1180-0636	CONFIDENTIAL	Status:	Final	
EudraCT No.: 2016-000878-38		Page:	20 of 29	

Change from baseline in nocturnal SMPG measurements will be assessed by considering the difference between PG values available at bedtime, at 4 AM and the before breakfast value the following day: (4 AM PG value minus at bedtime PG value), (before breakfast PG value minus at bedtime PG value) and (before breakfast PG value minus 4 AM PG value).

Change from baseline in nocturnal SMPG measurements 16 weeks after randomisation will be analysed based on all planned post baseline measurements until or at 16 weeks after randomisation using a model similar to 1) except with the corresponding baseline values as covariate.

If a subject achieves PPG target (based on overall mean of daily PPG measurements in 7-9-7-point SMPG profile) 16 weeks after randomisation:

Overall PPG (1 hour) \leq 7.8 mmol/L [140 mg/dL]

A dichotomous (responder / non-responder) endpoint will be defined based on whether a subject has reached an overall mean 1 hour PPG \leq 7.8 mmol/L [140 mg/dL] 16 weeks after randomisation, where PPG is derived from the 7-9-7-point SMPG profile.

This responder endpoint will be analysed based on a logistic regression model using treatment, region and metformin use at baseline (Yes/No) as factors, and baseline overall 1-hour mean PPG as covariate. In analysis of the in-trial observation period subjects without an overall mean 1 hour PPG at week 16 will be treated as non-responder. In the on-treatment observation period analysis subjects who discontinue randomised treatment, initiate ancillary treatment, withdraw from trial, or have no 1-hour mean PPG measurement at week 16 will be included as non-responders.

Overall PPG (1-hour) ≤7.8 mmol/L [140 mg/dL] without severe hypoglycaemia

A dichotomous (responder / non-responder) endpoint will be defined based on whether a subject has reached an overall 1-hour PPG ≤7.8 mmol/L [140 mg/dL] 16 weeks after randomisation without any treatment emergent severe hypoglycaemic episodes.

This responder endpoint will be analysed based on a logistic regression model using treatment, region and metformin use at baseline (Yes/No) as factors, and baseline mean 1-hour PPG as covariate. In analysis of the in-trial observation period subjects without an overall mean 1 hour PPG at week 16 will be treated as non-responders. In the on-treatment observation period analysis subjects who discontinue randomised treatment, initiate ancillary treatment, withdraw from trial, or have no 1-hour mean PPG measurement at week 16 will be included as non-responders.

Statistical Analysis Plan Trial ID: NN1218-4113 UTN: U1111-1180-0636

EudraCT No.: 2016-000878-38

CONFIDENTIAL

Date: Version: Status: Page:

12 February 2019 | Novo Nordisk Final 21 of 29

Insulin dose (Units/day and Units/kg/day; total basal, total bolus, total daily insulin dose and individual meal insulin dose) 16 weeks after randomisation

The insulin doses will be summarised descriptively by treatment week according to regimen, both by meal type and as total daily dose in units and units/kg (total daily and separately for each mealtime dose). Insulin doses will be summarised using the on-treatment observation period and using the safety analysis set.

Lipids-lipoproteins profile 16 weeks after randomisation

Lipid endpoints (total cholesterol, HDL cholesterol, LDL cholesterol) will be logarithmically transformed and analysed separately based on all planned post baseline measurements until or at 16 weeks after randomisation using a model similar to 1) except with the corresponding logtransformed baseline measurement as covariate. Estimated treatment means and the estimated treatment difference with corresponding 95% CI will be back-transformed to the original scale, resulting in estimated geometric means, a treatment ratio and a 95% CI for the treatment ratio.

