1.2 Scope of the statistical analysis plan

This statistical analysis plan (SAP) is based on the protocol *Efficacy and Safety of Fast-acting Insulin Aspart Compared to NovoRapid*[®] *both in Combination with Insulin Degludec with or without Metformin in Adults with Type 2 Diabetes (onset*[®] *9*), version 4.0 (dated 23 February 2018). The statistical analyses and derivations of endpoints presented in this SAP are almost identical to those described in the protocol. It contains minor clarifications for derivations, calculation of endpoints and analyses as well as some additions.

The changes to the statistical considerations proposed in this SAP and the reasons for the changes are described in section $\underline{3}$ and will be reported in the clinical trial report (CTR).

Statistical Analysis Plan Trial ID: NN1218-4113 UTN: U1111-1180-0636 EudraCT No.: 2016-000878-38

CONFIDENTIAL

Date: Version: Status: Page:

12 February 2019 | Novo Nordisk Final 6 of 29

Statistical considerations 2

General considerations

In general, for endpoints evaluated as a change from baseline and/or where a baseline adjustment is made, baseline is defined as information collected at randomisation (Visit 14). In case a measurement is not available at randomisation, the most recent measurement prior to randomisation will be used as baseline.

Two observation periods are defined, "in-trial" and "on-treatment", and it will be specified which period each analysis will use.

- In-trial: The observation period from date of randomisation and until last trial -related subject-site contact. The in-trial observation period includes data collected after treatment discontinuation.
- On-treatment: The observation period from date of first dose of randomised NovoRapid[®]/faster aspart and to 7 days after the first occurrence of:
 - The day of last dose of randomised NovoRapid ®/faster aspart
 - The day before initiation of ancillary treatment

All efficacy endpoints will be summarised and analysed using the full analysis set (FAS), unless otherwise stated. Safety endpoints will be summarised using the safety analysis set and analysed using the FAS, unless otherwise stated. The FAS and safety analysis set are defined in section 2.2.

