2.4.2.2 Safety endpoints

In terms of AEs, as a minimum, SAEs will be tabulated separately using the in-trial observation period.

All events in the in-trial observation period will be listed with information about whether it appeared in the on-treatment observation period or not.

Number of treatment emergent adverse events

Adverse events (AEs) will be coded using the Medical Dictionary for Regulatory Activities (MedDRA). AEs will be presented based on system organ class and preferred terms.

A Treatment Emergent Adverse Event (TEAE) is defined as an event that has an onset date on or after the first day of exposure to randomised treatment, and no later than seven days after the last day of exposure to randomised treatment.

TEAEs are summarised descriptively, whereas AEs not defined as treatment emergent are presented in listings, including AEs reported in the 30-day follow-up period. The summaries of TEAEs are made displaying the number of subjects with at least one event, the percentage of subjects with at least one event, the number of events and the event rate per 100 patient years of exposure. These summaries are done by seriousness, severity, relation to insulin treatment, relation to technical complaint, premature treatment discontinuation due to AEs, and outcome.

Furthermore, summary tables based on system organ class and preferred terms are made for:

All TEAEs

- Serious TEAEs
- Possibly or probably related TEAEs
- Severe TEAEs
- TEAEs with preferred term that are experienced by at least 5% of the subjects in any treatment arm or by at least 5% of all subjects

For AEs where additional information is recorded, this will be listed.

AEs occurring during the run-in period are considered non-treatment emergent and will be summarised separately.

Number of treatment emergent injection site reactions

Treatment emergent injection site reactions occurring during the trial will be summarised and listed.

Classification of Hypoglycaemia

Treatment emergent: hypoglycaemic episodes will be defined as treatment emergent if the onset of the episode occurs on or after the first day of exposure to randomised treatment, and no later than one day after the last day of exposure to randomised treatment.

Nocturnal hypoglycaemic episodes: episodes occurring between 00:01 and 05.59 both inclusive.

[figure not shown]

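### In the in-trial analyses of the two target-without-severe-hypoglycaemia composites, glucose is judged at week 16 but severe hypoglycaemia is counted only to one day after the last randomised dose

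*SAP*

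**What the plan says.** SAP 2.4.2.1 sets the analysis period for the supportive efficacy endpoints: "All endpoints except insulin dose in this section will be assessed using the FAS and the in-trial observation period", with a repeat on the on-treatment period. SAP section 2, General considerations, describes the first of these: "The in-trial observation period includes data collected after treatment discontinuation".

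The two composites share one structure. The HbA1c version requires HbA1c below 7.0% "16 weeks after randomisation without treatment emergent severe hypoglycaemic episodes". The SMPG version requires an overall 1-hour PPG of at most 7.8 mmol/L at week 16 "without any treatment emergent severe hypoglycaemic episodes".

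For the in-trial analysis the only further route to non-response is a missing glucose value. For HbA1c: "In the analysis of the in-trial observation period subjects without an HbA_{1c} measurement at week 16 will be treated as non-responders". For PPG: "In analysis of the in-trial observation period subjects without an overall mean 1 hour PPG at week 16 will be treated as non-responders". Stopping randomised treatment does not make a subject a non-responder here. In the on-treatment repeat it does.

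The hypoglycaemia window is set in SAP 2.4.2.2. An episode is treatment emergent if it starts on or after the first day of randomised exposure and "no later than one day after the last day of exposure to randomised treatment".

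Protocol version 4.0, sections 17.4.2.1 and 17.4.2.2, has the same definitions. The endpoint list in Protocol 4.2.2.2 names the composites without the treatment-emergent limit.

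**The concern.** A composite responder is easiest to interpret when its parts are assessed over the same period. Here one part includes data after treatment stops and the other does not. The earlier a subject stops while staying in the trial, the shorter the time in which that subject can fail on hypoglycaemia, although the glucose part is still read at week 16.

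For these subjects the gap works in one direction only: it can keep someone as a responder and can never remove one. What is at stake is the meaning of two supportive responder percentages and their odds ratios. A reader would naturally take the in-trial figure as target reached at week 16 with no severe hypoglycaemia up to then.

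**Working it through.** **Step 1. The two parts side by side, in-trial analysis**

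| Part | Period covered | Source |
|---|---|---|
| HbA1c or 1-hour PPG | Week-16 value, on or off randomised treatment | SAP 2, 2.4.2.1 |
| Severe hypoglycaemia | First randomised dose to one day after the last | SAP 2.4.2.2 |

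For a subject who completes treatment, the hypoglycaemia window reaches end of treatment at Visit 30, so the periods match. In the on-treatment repeat, discontinuers are non-responders and the question does not arise. It is confined to the in-trial analysis of subjects who stop early, stay in the trial and have a week-16 value. SAP 1.1 and Protocol 8.1.9 keep such subjects on planned visits to week 16. When Visit 30A falls within two weeks of Visit 30, only Visit 30A is held and its value is reallocated to week 16, so the two windows then nearly coincide.

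**Step 2. A worked record (hypothetical)**

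Randomised treatment is stopped at week 4, a severe episode occurs at week 10, and HbA1c is 6.8% at week 16. HbA1c is present and below 7.0%. The episode falls after the treatment-emergent window. By the rules as written this is an in-trial responder.

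**Step 3. How many subjects could be affected**

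The plan states no figure for this, so there is none to reproduce. Inputs from SAP 2.1: FAS of 1072 (536 per arm), treatment discontinuation of 10%, half of it trial discontinuation.

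- Stop treatment: 0.10 × 1072 = 107.2
- Leave the trial: 0.05 × 1072 = 53.6
- Off treatment but still in the trial: 107.2 − 53.6 = 53.6, about 54 subjects, 27 per arm, 5.0% of the FAS

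SAP 2.1 says discontinuation might be as low as 10%, so 54 is a planning figure and not a ceiling. The results below scale in proportion to it.

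**Step 4. How many would change status**

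The documents give no rate of severe hypoglycaemia, no responder rate and no time off treatment. Assumed ranges: rate r of 5 to 50 episodes per 100 patient-years, time off treatment t of 4 to 16 weeks, share at target s of 20% to 50%.

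Expected number = 53.6 × [1 − exp(−r × t/52)] × s, with r per patient-year.

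- Low: 53.6 × [1 − exp(−0.05 × 4/52)] × 0.20 = 0.04
- Middle: 53.6 × [1 − exp(−0.20 × 8/52)] × 0.50 = 0.81
- High: 53.6 × [1 − exp(−0.50 × 16/52)] × 0.50 = 3.82

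The high value is 3.82/1072 = 0.36 percentage points of the FAS, or 3.82/536 = 0.71 points if every such subject were in one arm. It requires all 54 to be off treatment for the full 16 weeks.

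**Step 5. Whether the data exist**

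Protocol 8.1.9 (version 4.0) requires hypoglycaemic episodes after discontinuation to be recorded in the diary and transcribed to the eCRF. Protocol 8.6.3 provides a diary for this purpose, and Protocol 8.4.2 records whether the subject could self-treat, which identifies a severe episode.

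**The case against.** The strongest reply is that the definition is explicit. SAP and protocol agree, a programmer has only one reading, and hypoglycaemia is analysed in the treatment-emergent window throughout SAP 2.4.2.2. Surveillance also thins after discontinuation: weekly contacts give way to the planned visits at weeks 4, 8, 12 and 16 plus follow-up, and daily 4-point profiles stop. Restricting the safety part to the period of comparable surveillance is defensible. In addition, severe episodes that qualify as SAEs are still tabulated over the in-trial period.

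Much of this stands. It shows that the restriction is not a slip in wording and that later serious episodes are not lost from the report. It does not bring the two parts of the in-trial composite onto one period. The question of hypoglycaemia on randomised treatment is already answered by the on-treatment repeat. SAP section 3 explains why ancillary treatment was added to the on-treatment responder rule but gives no reason for a mixed window in the in-trial version. The SAE tabulation does not change responder status and omits severe episodes that are not SAEs.

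A reader might infer three stronger things that the documents do not support:

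- **That the SAP promises a composite irrespective of discontinuation and breaks that promise.** The estimand wording to that effect covers change in HbA1c and is extended only to the two confirmatory secondary endpoints, not to supportive responders.
- **That these subjects are classified in error.** They are classified as the endpoint is defined; the issue is which window suits an in-trial analysis.
- **That one arm is favoured.** No imbalance is documented, and SAP 2.1 expects similar withdrawal reasons in the two arms.

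**Conclusion.** The point holds as a minor mismatch. In the in-trial analyses of the two composites, the glucose and hypoglycaemia parts cover different periods for subjects who stop randomised treatment early and remain in the trial, and nothing elsewhere in the SAP or protocol aligns them.

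On the SAP's planning assumption about 5% of the FAS is exposed. The change in status is roughly 0 to 4 subjects; that range rests wholly on assumed severe-episode rates, time off treatment and responder shares. The endpoints lie outside the four-step testing hierarchy. No primary, confirmatory or on-treatment result depends on this.

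**What to change.** In SAP 2.4.2.1, add one sentence covering the in-trial analyses of both composites: any severe hypoglycaemic episode from the date of randomisation to the week-16 assessment makes the subject a non-responder. Keep the treatment-emergent definition for the on-treatment repeat. The window should start at randomisation, because the in-trial period starts there and the FAS includes all randomised subjects; a start at first dose would leave a randomised but undosed subject with no window at all.

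No new data collection is needed. The in-trial responder percentage may be slightly lower. Because surveillance after discontinuation is less frequent than the weekly contacts on treatment, some later episodes may still be missed, and the report should say so. If the sponsor prefers the present definition, the SAP should state that the hypoglycaemia part is deliberately limited to randomised treatment in the in-trial version too.
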